6.1.4. Dose Modification Guidelines for KZR-616

6.1.4.1. Dose Reduction

Patients who experience a KZR-616-related AE are permitted to undergo dose reduction of KZR-616 in a blinded manner for subsequent doses at the discretion of the Investigator or upon recommendation by the DMC as per [Section 8.1.2](#); written Medical Monitor approval must be obtained in advance of implementing dose reduction. Any dose modifications should be documented in the eCRF as per [Section 9.1.4](#). Patients must continue to fulfill the Dosing Criteria in [Section 6.1.1](#) prior to each dose. After dose reduction is implemented, patients who are currently on treatment with KZR-616 will remain on 30 mg throughout the relevant Treatment Period if the dose reduction occurs at W1 (Treatment Period 1) or W17 (Treatment Period 2); they will have their dose reduced to 30 mg from 45 mg if the dose reduction occurs at or after W2 (Treatment Period 1) or W18 (Treatment Period 2). Once the dose has been reduced, it will remain at the reduced dose level only for the duration of the Period during which the dose was reduced.

6.1.4.2. Missed Doses

Doses should be administered within the visit windows as per the Schedules of Assessments ([Section 7.1](#)). Any doses administered outside of the visit window will be considered a protocol deviation, but if necessary to avoid missing a dose, doses can be administered up to 3 days from the date of scheduled administration per [Section 7.1](#) with a minimum of 4 days required between doses.

Patients who do not fulfill Dosing Criteria ([Section 6.1.1](#)) or who meet Individual Patient Stopping Rules ([Section 8.1.2](#)) may miss up to 2 consecutive doses, or patients may miss up to 4 total doses for any reason (eg, AE, scheduling, emergency). Upon resumption of dosing, subsequent doses should be timed according to the original dosing schedule based on Day 1. If more than 2 consecutive doses or more than 4 total doses were missed, then the patient should be discussed with the Medical Monitor to evaluate if KZR-616 should be discontinued. Any dose modifications should be discussed with the Medical Monitor and documented in the eCRF as per [Section 9.1.4](#). Patients who are discontinued for missed doses should have their discontinuation per [Section 8.2](#) recorded in the eCRF based on the reason the doses were missed, eg, AE, protocol noncompliance.

If study medication is permanently discontinued due to an AE, the planned assessments (see Schedule of Assessments) should continue for the protocol specified time period.

6.2. Prior and Concomitant Treatments

Any concomitant therapies must be recorded on the eCRF. A concomitant therapy is any therapy that may be used, eg, transfusions, physical therapy, surgery, medication. A concomitant medication is any prescription or over-the-counter preparation, including vitamins and supplements. Except as described below, prior and concomitant medication use will be recorded for the 60 days prior to screening until the last follow-up visit. Details to be recorded include, but are not limited to, the concomitant medication generic name, dose, route, frequency of administration, and indication. Prior to study initiation, the Sponsor will specify which version of the drug dictionary is to be used.

All prior DM/PM medications (eg, corticosteroids, immunosuppressants, antimalarials, biologics) regardless of time frame of use will be recorded.

Background medication(s) will not be provided by the Sponsor unless required by local legislation.

6.2.1. Permitted Concomitant Medications

6.2.1.1. Myositis Disease-related Concomitant Medications

Patients should continue all concomitant medications related to myositis therapy throughout the study, as outlined in the Inclusion/Exclusion Criteria ([Section 4.2](#) and [Section 4.3](#)) at a stable dose, without modification throughout the study, unless there is documented toxicity, intolerance, or lack of availability. No new immunomodulatory therapies, including investigational agents, are permitted to be introduced during the study. If a concomitant treatment for myositis needs to be decreased or discontinued for safety reasons, the reason must be documented in the eCRF and should be discussed with the Medical Monitor (and discussed in advance where possible).

The permitted medications for myositis include the use of the following:

- Oral prednisone (or prednisone equivalent) dose ≤ 20 mg/day. If used, it must have been present at Screening, used at a stable dose for the 2 weeks prior to Baseline.
- The use of a maximum of 1 of the following immunosuppressants is allowed:
 - Oral MMF or MPS (≤ 3 g/day or 2160 mg/day, respectively)
 - Oral, IM, or SC MTX (≤ 25 mg/week)
 - Oral AZA (≤ 2.5 mg/kg/day)
 - LEF (≤ 20 mg/day)
 - Tacrolimus (≤ 3 g/day).

If a permitted immunosuppressant is being used, it must have been used for at least 12 weeks and must have been taken at a stable dose (including stable route of administration) for the last 4 weeks prior to Screening.

- The use of the following antimalarials is allowed if present at a stable dose for at least 12 weeks prior to Screening:
 - Hydroxychloroquine up to 400 mg/day or 6.5 mg/kg/day, whichever is less
 - Chloroquine up to 250 mg/day
 - Quinacrine up to 100 mg/day.
- Continued use of a stable dose of topical therapy (eg, corticosteroids, pimecrolimus) is allowed.

6.2.1.2. Other Concomitant Medications

Hormonal contraception is allowed; if used by a WOCBP, it should be used and have been stable as described in [Section 4.2](#) and continued for the duration of the study. If hormonal contraception is discontinued for safety reasons, the Investigator should ensure that the patient is using another acceptable form of contraception.

Other concomitant therapies for comorbid conditions, such as antihypertensives or lipid lowering agents, are permitted. The patient should be advised to maintain a stable dosage regimen for lipid lowering agents (such as statins) and nonsteroidal anti-inflammatory drugs (NSAIDs) unless dosage adjustment is clinically necessary.

KZR-616 is a substrate of the P-glycoprotein (P-gp) transporter. Given the rapid clearance of the drug (half-life <2 hours), it is unlikely that inhibitors of P-gp will affect drug exposure. However, no formal interaction studies with P-gp inhibitors have been performed. Therefore, KZR-616 should be administered at least 4 hours after drugs that are known inhibitors of P-gp (eg, atorvastatin, azithromycin, colchicine, omeprazole).

6.2.1.3. Vaccinations

It is strongly recommended that patients be up-to-date on immunizations per the Centers for Disease control (<https://www.cdc.gov/vaccines/schedules/hcp/imz/adult.html>) or current 2015 American College of Rheumatology guidelines for RA. Vaccinations received at any time documenting that the patient is up to date on vaccines should be recorded in the eCRF.

Note: Patients who received a live-attenuated vaccine within 4 weeks of Screening will be excluded from participation in the study as per [Section 4.3](#).

6.2.2. Rescue Therapy

Rescue therapy is defined as any modification to the background DM or PM treatment, including dose or frequency increases of concomitant medications or initiation of a new medication. Rescue medications may include, but are not limited to IVIg, topical calcineurin inhibitors, systemic corticosteroids, or nonsteroidal immunosuppressants. While rescue therapy is typically restricted or prohibited therapy per protocol ([Section 6.2.3](#)), patients may receive rescue therapy during the study at the discretion of the Investigator when deemed medically necessary for the safety of the patient, eg, hospitalization for worsening DM or PM.

If an Investigator determines that a patient needs rescue therapy, the Medical Monitor should be informed; where possible, a discussion should occur between the Investigator and Medical Monitor prior to implementation of the rescue therapy.

Any rescue medications administered should be recorded in the eCRF under concomitant medications. Patients who receive rescue therapy may continue in the study upon Medical Monitor approval but will be considered nonresponders from the timepoint of receipt or rescue therapy forward (as per [Section 6.2](#)).

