2.2. Study Endpoints

2.2.1. Efficacy Endpoints

The primary efficacy endpoint is:

- Mean change from start to end of KZR-616 treatment in the Total Improvement Score (TIS), which ranges from 0 to 100.

Secondary efficacy endpoints are:

- Proportion of patients with an increase ≥ 20 points on the TIS from start to end of KZR-616 treatment. The categories and ranges of scores for improvement are: 20-39 points being minimal improvement, 40-59 points being moderate improvement, and ≥ 60 points being major improvement
- Proportion of patients from start to end of KZR-616 treatment meeting International Myositis Assessment and Clinical Studies Group (IMACS) Definition of Improvement (DOI). The IMACS DOI is $\geq 20\%$ improvement in at least 3 of 6 core set activity measures, with no more than 2 core set activity measures (CSAMs) worsening by $\geq 25\%$ (the Manual Muscle Testing-8 Muscle Groups [MMT-8] cannot be a worsening measure)
- Absolute change and percent change from start to end of KZR-616 treatment in the IMACS individual CSAMs
- For patients with DM, the mean change from start to end of KZR-616 treatment in the Cutaneous Dermatomyositis Disease Area and Severity Index (CDASI)
- For patients with DM, the mean change from start to end of KZR-616 treatment in the Peak Pruritus Numeric Rating Scale (NRS).

Exploratory efficacy endpoints are:

- Mean change over time from start to end of KZR-616 treatment in the TIS in all patients, patients with DM only, and in patients with PM only
- Proportion of patients over time with an increase of ≥ 20 , ≥ 40 , or ≥ 60 points on the TIS from start to end of KZR-616 treatment in all patients, in patients with DM only, and in patients with PM only
- For patients with an increase of ≥ 20 points on the TIS from Baseline to W16, the proportion of patients with no change or increase in their TIS at W32 for all patients, in patients with DM only, and in patients with PM only
- Mean change and mean percent change over time from start to end of KZR-616 treatment in the IMACS individual CSAMs and core set damage measures (CSDMs) for all patients, in patients with DM only, and in patients with PM only
- Mean change from Baseline over time from start to end of KZR-616 treatment in the FI-2, the FI-3 and the individual components of the FI-3 for all patients, in patients with DM only, and in patients with PM only
- For patients with DM, mean change over time from start to end of KZR-616 treatment in the CDASI

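### The rescue definition is wide enough that a permitted decrease in background treatment could be scored as nonresponse, with no reset at Week 16

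*Combined protocol and SAP*

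**What the plan says.** Section 6.2.2 gives the definition: "Rescue therapy is defined as any modification to the background DM or PM treatment". Raised doses and newly started drugs are then introduced as inclusions, so on the grammar they illustrate the definition and do not close it. The same section says that patients who receive rescue may stay in the study with Medical Monitor approval but "will be considered nonresponders from the timepoint of receipt or rescue therapy forward".

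Section 6.2.1.1 asks for background myositis drugs to be kept stable, "without modification throughout the study, unless there is documented toxicity, intolerance, or lack of availability". It then foresees reductions and stops: "If a concomitant treatment for myositis needs to be decreased or discontinued for safety reasons, the reason must be documented in the eCRF". It also asks for discussion with the Medical Monitor. It says nothing about how such a patient is scored.

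Two secondary endpoints in Section 2.2.1 are responder proportions. One is "Proportion of patients with an increase ≥ 20 points on the TIS from start to end of KZR-616 treatment". The other is the proportion meeting the IMACS definition of improvement. Section 10.3 summarises binary endpoints by count, percentage and Clopper-Pearson interval, and Section 10 does not mention rescue. Section 6.2.2 cites Section 6.2 for the nonresponder rule, but the introduction to Section 6.2 contains no such rule.

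**The concern.** A decrease or a stop is a modification, and Section 6.2.1.1 itself uses that word for the changes it permits. Put together, the two sections can turn a permitted, safety-driven reduction into rescue, and rescue into nonresponse. A patient who improves on less background treatment would then count as a treatment failure, which reverses the usual reason for a rescue rule: to avoid crediting the study drug with the effect of added therapy.

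The crossover design adds a second problem. The status runs forward and nothing ends it at Week 16. For Arm B, the KZR-616 period is the second one, so an event under placebo could settle the KZR-616 outcome before the first active dose.

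Such events are foreseeable. Section 6.2.1.1 provides for them, and inclusion criterion 6 admits patients with documented toxicity from, or intolerance to, corticosteroids or immunosuppressants. At stake are the two secondary responder proportions, the exploratory TIS proportions at 20, 40 and 60 points and, for DM, the CDASI proportion.

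**Working it through.** **1. The plan's own figure.** Section 10.1 gives 24 patients, two-sided alpha 0.05, 80% power at effect size 0.6, 90% at 0.7, and a smallest significant observed effect of 0.42. For a paired t-test with 23 degrees of freedom and noncentrality d × √24:

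- d = 0.6: power 80.4%
- d = 0.7: power 90.7%
- smallest significant effect = t(0.975, 23)/√24 = 0.422

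All three reproduce. The calculation uses no responder status and no rescue rate, so the rescue wording does not alter it.

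**2. The sections side by side.**

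| Background change | Section 6.2.1.1 | Section 6.2.2, read literally | Section 6.2.2, read as escalation only |
|---|---|---|---|
| Dose increase or new myositis drug | Not permitted | Rescue; nonresponder | Rescue; nonresponder |
| Decrease or stop for safety | Permitted; reason in eCRF | Rescue; nonresponder | Not rescue; scored on data |
| Change because of lack of supply | Permitted | Rescue; nonresponder | Depends on direction of change |

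The second row shows that two analysts could score the same patient differently while each follows the text.

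**3. Reach across periods.** Under Sections 2.2.1 and 10.3, the KZR-616 period is W0 to W16 in Arm A and W16 to W32 in Arm B.

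- Arm A: only a change before W16 can affect the KZR-616 response. A later change, under placebo, comes too late.
- Arm B: a change at any time from W0 to W32 can affect it. If the decrease occurs before W16 and background is stable afterwards, the W16 starting value and the W32 value are both taken on the reduced background, yet the patient is still a nonresponder for the whole active period.

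The exposure is therefore 16 weeks in Arm A and 32 weeks in Arm B. The carry-over of status arises for true escalation in Period 1 as well, so narrowing the definition alone does not settle it.

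**4. Size per patient.** If all 24 are evaluable, one reclassified responder moves the pooled rate by 1/24 = 4.2 percentage points. In the Week 0 to 16 comparison, with about 12 per arm, it moves that arm's rate by 1/12 = 8.3 points.

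**5. Illustration.** The documents give neither a response rate nor a rate of decreases, so both are assumed here. Starting from 12 of 24 responders:

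| Reclassified | Rate | 95% Clopper-Pearson |
|---|---|---|
| 0 | 12/24 = 50.0% | 29.1 to 70.9 |
| 1 | 11/24 = 45.8% | 25.6 to 67.2 |
| 2 | 10/24 = 41.7% | 22.1 to 63.4 |
| 3 | 9/24 = 37.5% | 18.8 to 59.4 |

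With three reclassified, an assumed 8/24 falls from 33.3% to 20.8%, and an assumed 16/24 from 66.7% to 54.2%.

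**The case against.** The best reply is that Section 6.2.2 as a whole is about treatment that is added. Its examples are increases and new drugs, and the medications it names are ones a patient is given. It describes rescue as normally restricted or prohibited under Section 6.2.3, which lists no decrease or stop. Its example trigger is worsening disease, and Section 1.5 also links rescue to worsening. The nonresponder rule attaches to receiving rescue, and a dose cut is not naturally received. Section 6.2.1.1 can then be seen as the separate pathway for decreases.

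This is persuasive on intent, and it stands to that extent. A reader might infer from the definition that every permitted decrease does make the patient a nonresponder; the documents do not support so firm a statement. But intent does not remove the conflict. The definition is not limited to escalation, no exception is written, and Section 10 does not resolve it. The detailed SAP that Section 10 announces is not in the documents, so whether it resolves the matter cannot be checked.

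It can also be said that any error lowers the KZR-616 rate and so cannot create a false benefit. That holds for the pooled KZR-616 proportion. It does not hold for a Week 0 to 16 comparison of responder rates: a placebo patient wrongly scored as a failure widens the difference in favour of KZR-616 by about 8.3 points.

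Finally, no frequency is given, and the per-patient figures would apply to any misclassification. That is correct. They show sensitivity at this sample size, not expected bias.

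**Conclusion.** The concern holds as a conflict between Sections 6.2.2 and 6.2.1.1 that could misclassify patients on the responder endpoints. Applied literally, the rule counts improvement after a permitted decrease as failure, and in Arm B it can carry a placebo-period event into the KZR-616 result. The size is 4.2 points of the pooled rate per affected responder, or about 8.3 points of one arm's rate if the responder endpoints are also compared over Weeks 0 to 16. These figures assume 24 evaluable patients, 12 per arm; how many would be affected is unknown.

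A reader might go further and infer that the primary result is biased or underpowered. The documents do not support that. The primary endpoint is a continuous change in TIS tested by a paired t-test, no text says how nonresponder status enters it, and the stated power reproduces without it. The point merits correction before unblinding because, with so few patients, the choice of reading should not be made after the data are seen.

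**What to change.** Reconcile Sections 6.2.1.1 and 6.2.2. Then, before unblinding, put one scoring rule in Section 10 or the SAP that states:

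- which changes in background treatment trigger nonresponder status, so that permitted safety-driven decreases or stops are not scored as failure by default, and how changes for lack of supply are handled;
- whether the status carries across W16 or is assessed afresh in each treatment period;
- which endpoints the rule applies to.

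Correct the cross-reference to Section 6.2 so that it points to the place where the rule stands. Use the eCRF reason already required for safety-driven decreases and stops to flag these patients and list them separately, and record the reason for supply-driven changes in the same way.

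The cost is a few sentences and a matching data flag, with no change to sample size or visits. This concerns endpoint scoring only; it does not change what treatment patients may receive or when.

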6.2.2.1. Nonpharmacologic Therapies

Patients who are receiving physical or occupational therapy or exercising should have had a stable treatment or exercise regimen for at least 4 weeks prior to Screening as per [Section 4.3](#) and remain on a stable regimen throughout the duration of the study. A regimen should not be initiated during the study.

6.2.3. Restricted or Prohibited Therapies

Use of the following is prohibited during the study and as described in [Section 4.3](#):

- Oral prednisone (or prednisone equivalent) doses >20 mg/day
- Intravenous or IM corticosteroids
- Initiation of IV, SC, or IM Ig
- Immunosuppressants (other than as presented in [Section 6.2.1](#))
- Antimalarials at doses that exceed the recommended dose (see [Section 6.2.1](#))
- Topical therapy (other than as presented in [Section 6.2.1](#))
- Intra-articular therapy (eg, corticosteroids or hyaluronic acid preparations)
- Cyclophosphamide or chlorambucil
- Nonbiologic immunosuppressants or targeted therapies including, but not limited to, CyA, dapsone, tofacitinib, baricitinib
- Cytokine or integrin antagonists or selective costimulation modulators including, but not limited to, IL-1, IL-6, IL-17, IL-12/23, IL-23, IFN, integrin, and TNF α antagonists or abatacept
- B cell-depleting or modulating therapies (eg, rituximab, ofatumumab, obinutuzumab, ocrelizumab, belimumab, atacicept)
- Cell-depleting therapies, including investigational agents or approved therapies, alemtuzumab, anti-CD4, anti-CD5, or anti-CD3
- Any other biologics or investigational drug(s)
- Transfusion with blood, packed red blood cells, or platelets or treatment with plasmapheresis or plasma exchange
- Creatine dietary supplements
- Live-attenuated vaccines
- Major surgery during the study period, or any surgery planned during the study period that would require an alteration of concomitant immunosuppressant or corticosteroid therapy or additional corticosteroid therapy.

6.2.4. Other Restrictions and Prohibitions

Participants should not donate blood or blood products during the study and continuing through 4 weeks after administration of the last dose of the study drug. Female participants should not donate eggs during the study and continuing through 4 weeks after administration of the last dose of the study drug. Male participants should not donate sperm during the study and continuing through 12 weeks after administration of the last dose of the study drug.

7. STUDY EVALUATIONS

7.1. Schedules of Assessments

The Schedule of Assessments for Screening and Treatment Period 1 is presented in [Table 2](#) and the Schedule of Assessments for the study drug administration visits during Treatment Period 1 is presented in [Table 3](#).

The Schedule of Assessments for Treatment Period 2, the ETV, and SFU is presented in [Table 4](#) and the Schedule of Assessments for the study drug administration visits during Treatment Period 2 is presented in [Table 5](#).

Please refer to the Laboratory Manual for details regarding the specific blood draw requirements for each visit.

For details regarding visit windows, refer to the Schedule of Assessments ([Table 2](#), [Table 3](#), [Table 4](#), and [Table 5](#)).

7.1.1. Unscheduled Visits

All attempts should be made to keep patients on the study schedule. Unscheduled visits may be necessary to repeat testing following abnormal laboratory results, for follow-up of AEs, or for any other reason, as warranted. During an unscheduled visit, the following information will be required to be collected:

- Concomitant medications
- AEs

Any of the other procedures listed for the W32 visit may also be performed at the Investigator's discretion.

Table 2 Schedule of Assessments for Screening and Treatment Period 1

Study Period	Screening	Treatment Period 1			
Visit Number	1	2	6	10	14
Start of Week	-4	0	4	8	12
Day ± Window	-28 to -1	1	29±1	57±1	85±1
PK and PD assessments		Predose	Postdose		
Informed consent	X				
Informed consent for genotyping	X				
Informed consent for biopsies	X				
Inclusion/exclusion criteria ^a	X	X			
Demographic data	X				
PM and DM classification criteria ^b	X				
Medical history (including procedures, prior therapy, social history)	X				
Concomitant therapy			↔		
Randomization		X			
Tuberculosis assessment ^c	X				
Viral serology (HIV/HBV/HCV) ^d	X				
Chest radiograph ^e	X				
Follicle stimulating hormone ^f	X				
Coagulation, thyroid, APLA ^g	X				
Pregnancy test ^h	X	X	X	X	X
Physical examination ⁱ	X	X		X	
Vital signs, weight, and height ^j	X	X	X	X	X
12-lead ECG ^k	X	X	X		X
MMT-8 ^l	X	X	X	X	X
MDAAT, MDGA, MDGIC ^l	X	X	X	X	X
FI-2 (dominant side only) ^l	X	X			
FI-3 ^l	X	X		X	
Sit-to-stand test ^l	X		X		X
MDI ^l	X	X			
CDASI ^{l, m}	X	X	X	X	X
PtGADA, HAQ-DI, PGIC ⁿ	X	X	X	X	X
PROMIS-29, EQ-5D-5L ⁿ	X	X	X		
HRU ⁿ		X		X	
PtGADD ⁿ	X	X			
Peak Pruritus NRS ^{m, n}	X	X	X	X	X
TSQM ⁿ			X		
Hematology, chemistry ^o , CRP, and aldolase	X	X	X	X	X

Study Period	Screening		Treatment Period 1		
	1	2	6	10	14
Visit Number	1	2	6	10	14
Start of Week	-4	0	4	8	12
Day ± Window	-28 to -1	1	29±1	57±1	85±1
PK and PD assessments		Predose	Postdose		
Erythrocyte sedimentation rate ^p	X	X		X	X
CD19 count ^q	X				
Urinalysis ^r	X	X		X	X
Quantitative immunoglobulins ^s	X	X			
Autoantibodies ^t	X				
PK assessment ^u		X	X		
PD assessment ^v		X	X		
Cytokines/proteomics and leukocyte subsets ^w		X		X	
Gene expression and DNA methylation profiling (RNA) ^x		X		X	
Genotyping (DNA) ^x		X			
Skin and/or muscle biopsies ^y	X				
Study drug administration ^z		X		X	X
Adverse events		←	→		

Abbreviations: APLA=antiphospholipid antibodies; CD19=cluster of differentiation 19; CDASI=Cutaneous Dermatomyositis Disease Area and Severity Index; CRP=C-reactive protein; DM=dermatomyositis; DNA=deoxyribonucleic acid; ECG=electrocardiogram; EQ-5D-5L=EuroQoL 5-dimension 5-level; FI-2=Functional Index-2; FI-3=Functional Index-3; HAQ-DI=Health Assessment Questionnaire-Disability Index; HBV=hepatitis B virus; HCV=hepatitis C virus; HIV=human immunodeficiency virus; HRU=healthcare resource utilization; MDAAT=Myositis Disease Activity Assessment Tool; MDGA=Physician Global Assessment; MDI=Myositis Damage Index; MDGIC=Physician Global Impression of Change; MMT-8=Manual Muscle Testing-8 Muscle Groups; NRS=numeric rating scale; PD=pharmacodynamics; PK=pharmacokinetics; PROMIS-29=Patient Reported Outcomes Measurement Information System 29-item Short Form Profile Version 2.1; PtGADA=Patient Global Assessment of Disease Activity; PtGADD=Patient Global Assessment of Disease Damage; PGIC=Patient Global Impression of Change; RNA=ribonucleic acid; TSQM=Treatment Satisfaction Questionnaire for Medication Version II.

Note: Chest radiograph and ECG (as well as other assessments approved by the Medical Monitor) may be performed as needed to confirm findings requiring confirmation on the MDAAT.

- Eligibility criteria for this study should be assessed only after signing of informed consent for this study. All data from Screening and all data except for central laboratory results from the Day 1 visit should be used to confirm patient eligibility.
- Classification criteria and web calculator located at: <https://www.niehs.nih.gov/research/resources/imacs/classificationcriteria/index.cfm>.
- Tuberculosis assessment includes an interferon gamma release assay. If indeterminate or borderline on first assessment, it may be repeated. A positive or second indeterminate result is exclusionary. Test may be performed locally or centrally.
- Human immunodeficiency viruses 1 and 2, hepatitis B virus core antibody and surface antigen, and hepatitis C virus antibody.
- Chest radiograph should be performed at Screening (posteroanterior view) if findings from a radiograph obtained within 12 weeks before Screening are not available.
- Follicle stimulating hormone may be drawn to confirm postmenopausal status in female patients.
- Coagulation: prothrombin time, international normalized ratio, activated partial thromboplastin time, lupus anticoagulant panel; thyroid function: thyroid stimulating hormone, free T4, free T3; APLA: antiphospholipid antibodies (anti-β₂ glycoprotein I IgG and IgM, anticardiolipin IgG and IgM).
- A serum pregnancy test should be performed at Screening and a urine pregnancy test will be performed at all other visits.
- A complete physical examination should be performed at Screening, Week 16, W32/Early Termination Visit, and End of Study Visit (see Table 4). Physical examinations at all other time points may be limited in nature.

- j. Vital signs and weight will be measured at all visits; height will be measured at Screening only. Blood pressure and pulse rate should be collected after the patient has had at least 5 minutes of rest in the seated position. If the blood pressure is elevated on the first measurement at Screening or Baseline, it should be repeated after an additional 5 minutes of rest. It is recommended that blood pressure is measured using the same arm at each assessment.
- k. 12-lead ECG should be performed after at least 5 minutes of rest in a supine position.
- l. Should be completed by qualified personnel, and it is recommended that the same individual performs the assessment at all visits.
- m. Should be performed only in those patients with DM.
- n. Patient reported outcome measures are recommended to be completed first at each visit where performed, ie, prior to any other procedures or assessments other than signing of informed consent.
- o. Hematology: hemoglobin, hematocrit, red blood cell count, mean corpuscular volume, mean corpuscular hemoglobin, mean corpuscular hemoglobin concentration, white blood cell count (total and differential), and platelet count.
Clinical chemistry: creatinine, creatine kinase, urea (or blood urea nitrogen), aspartate aminotransferase, alanine aminotransferase, gamma glutamyltransferase, alkaline phosphatase, lactate dehydrogenase, total bilirubin, albumin, total protein, sodium, potassium, chloride, glucose, uric acid, total cholesterol, magnesium, calcium, phosphorus.
- p. Erythrocyte sedimentation rate should be performed locally.
- q. CD19 count is required to be performed only for those patients being evaluated for eligibility who had their last dose of rituximab ≥ 24 and < 48 weeks before Screening.
- r. Urinalysis: color, appearance, specific gravity, pH, protein, glucose, ketones, bilirubin, blood, urobilinogen, nitrite, leukocyte esterase with reflex testing for microscopic parameters.
- s. Quantitative immunoglobulins: IgG, IgM, IgA.
- t. Autoantibodies could potentially include the following: myositis autoantibodies: anti-Jo-1, anti-PL-7, anti-PL12, anti-EJ, anti-OJ, anti-SRP, anti-Mi-2 α , anti-Mi-2 β , anti-MDA-5, anti-TIF-1 γ , anti-NXP-2, anti-HMGCR; other autoantibodies: anti-PM-Scl, anti-U1RNP, anti-SSA, anti-SSB, anti-Ku, anti-SAE, anticentromere, antinuclear.
- u. Pharmacokinetics will be performed as sparse sampling before dosing and at 0.5 (± 5 minutes) and 4 hours (± 10 minutes) after dosing in all patients at Week 0 and at Week 16 (see [Table 4](#)). In addition, a PK sample will be obtained at 0.25 (± 5 minutes), 1 (± 10 minutes), or 2 hours (± 10 minutes) after dosing at Weeks 0 and 16 (see [Table 4](#)) based on the random assignment of a patient via the Randomization and Trial Supply Management system to PK Cohort A, B, or C.
- v. Blood sampling for PD (proteasome inhibition) will be performed in all patients before dosing and at 4 hours after dosing at Week 0 and at Week 16 (see [Table 4](#)).
- w. Blood sampling will be performed before dosing to measure cytokines including IFN α , IFN β , IFN γ , IL-2, IL-6, IL-12, IL-17A, IL-21, IL-23, CXCL10, BLyS, TNF α , TGF β ; and to profile immune cells including B cell subgroups (naïve, activated, memory), plasma cell subgroups (long, short-lived), T cell subgroups (CD4 [Th1, Th17, all, naïve, activated], CD8 [memory], Treg).
- x. Will be performed in patients who have provided the proper informed consent for genetic analyses.
- y. Patients who do not have a muscle biopsy will be permitted to get one during the Screening Period if needed to determine eligibility. Skin and/or muscle biopsies for histology and gene expression analysis will be performed in consenting patients at qualified centers. Patients who agree to participate in the biopsy substudy will have biopsies obtained at the time points as specified.
- z. Patients need to be monitored for 2 hours after dosing at Week 0 and at Week 16 (see [Table 4](#)). Patients will receive study drug weekly. Home health service will be arranged for patients who choose not to return to investigative site for study drug administration weekly according to [Table 3](#).

Table 3 Schedule of Assessments for the Study Drug Administration Visits during Treatment Period 1

Study Period	Treatment Period 1											
	3	4	5	7	8	9	11	12	13	15	16	17
Visit No.	3	4	5	7	8	9	11	12	13	15	16	17
Start of Week	1	2	3	5	6	7	9	10	11	13	14	15
Day	8±1	15±1	22±1	36±1	43±1	50±1	64±1	71±1	78±1	92±1	99±1	106±1
Vital signs ^a	X	X	X	X	X	X	X	X	X	X	X	X
Study drug administration	X ^b	X	X	X	X	X	X	X	X	X	X	X

Note: Home health service will be arranged for patients who choose not to return to investigative site for study drug administration weekly.

- a. Vital signs will be collected before dosing. Blood pressure and pulse rate should be collected after the patient has had at least 5 minutes of rest in the seated position. It is recommended that blood pressure is measured using the same arm at each assessment.
- b. Patients need to be monitored for 2 hours after dosing at Visit 3.

Table 4 Schedule of Assessments for Treatment Period 2 and Safety Follow-up

Study Period	Treatment Period 2				SFU		
	18	22	26	30	34/ETV ^a	35	36/EOS
Visit No. and or Name	16	20	24	28	32	36	40
Start of Week							
Day	113±1	141±1	169±1	197±1	225±2	253±3	281±3
PK and PD assessments	Predose	Postdose					
Concomitant therapy							
Pregnancy test ^b	X		X	X	X		
Physical examination ^c	X			X	X		X
Vital signs and weight ^d	X		X	X	X	X	X
12-lead ECG ^e	X		X				X
MMT-8 ^f	X		X	X	X	X	X
MDAAT, MDGA, MDGIC ^f	X		X	X	X	X	X
FI-2 (dominant side only) ^f	X						X
FI-3 ^f	X			X			X
Sit-to-stand test ^f			X		X		X
MDI ^f	X					X	
CDASI ^g	X		X	X	X	X	X
PtGADA, HAQ-DI, PGIC ^h	X		X	X	X	X	X
PROMIS-29, EQ-5D-5L ^h	X		X				X
HRU ^h	X			X		X	X
PtGADD ^h	X					X	X
TSQM ^h	X		X			X	X
Peak Pruritus NRS ^{g,h}	X		X	X	X	X	X
Hematology, chemistry ⁱ , CRP, and aldolase	X		X	X	X	X	X
Erythrocyte sedimentation rate ^j	X		X	X	X	X	X
Urinalysis ^k	X		X	X	X	X	X
Quantitative immunoglobulins ^l	X					X	
Autoantibodies ^m	X					X	
PK assessment ⁿ	X	X					
PD assessment ^o	X	X				X	
Cytokines/proteomics and leukocyte subsets ^p	X		X			X	
Gene expression and DNA methylation profiling (RNA) ^q	X		X			X	
Skin and/or muscle biopsies ^r	X					X	
Study drug administration ^s	X ^s		X	X	X		
Adverse events							

Abbreviations: CDASI=Cutaneous Dermatomyositis Disease Area and Severity Index; CRP=C-reactive protein; DM=dermatomyositis; ECG=electrocardiogram; EOS=End of Study; EQ-5D-5L=EuroQoL 5-dimension 5-level; ETV=Early Termination Visit; FI-2=Functional Index-2; FI-3=Functional Index-3; HAQ-DI=Health Assessment Questionnaire-Disability Index; HRU=healthcare research utilization; MDGIC=Physician Global Impression of Change; MDAAT=Myositis Disease Activity Assessment Tool;

MDGA=Physician Global Assessment; MDI=Myositis Damage Index; MMT-8=Manual Muscle Testing-8 Muscle Groups; NRS=numeric rating scale; PD=pharmacodynamics; PK=pharmacokinetics; PROMIS-29=Patient Reported Outcomes Measurement Information System 29-item Short Form Profile Version 2.1; PtGADA=Patient Global Assessment of Disease Activity; PtGADD=Patient Global Assessment of Disease Damage; PGIC=Patient Global Impression of Change; RNA=ribonucleic acid; SFU=Safety Follow-up; TSQM=Treatment Satisfaction Questionnaire for Medication Version II.

Note: Chest radiograph and ECG (as well as other assessments approved by the Medical Monitor) may be performed as needed to confirm findings requiring confirmation on the MDAAT.

- a. Patients withdrawing prior to Week 32 visit should complete all Early Termination Visit (Week 32) assessments for their early termination visit. It is requested that these patients return for their Safety Follow-up Visit 9 weeks after administration of the last dose of the study drug.
- b. A urine pregnancy test will be performed.
- c. A complete physical examination should be performed at the W32/Early Termination Visit and End of Study Visit. Physical examinations at all other time points may be limited in nature.
- d. Vital signs and weight will be measured at all visits. Blood pressure and pulse rate should be collected after the patient has had at least 5 minutes of rest in the seated position. If the blood pressure is elevated on the first measurement at Screening or Baseline, it should be repeated after an additional 5 minutes of rest. It is recommended that blood pressure is measured using the same arm at each assessment.
- e. 12-lead ECG should be performed after at least 5 minutes of rest in a supine position.
- f. Should be completed by qualified personnel, and it is recommended that the same individual performs the assessment at all visits.
- g. Should be performed only in those patients with DM.
- h. Patient reported outcome measures are recommended to be completed first at each visit where performed, ie, prior to any other procedures or assessments other than signing of informed consent.
- i. Hematology: hemoglobin, hematocrit, red blood cell count, mean corpuscular volume, mean corpuscular hemoglobin, mean corpuscular hemoglobin concentration, white blood cell count (total and differential), and platelet count.
- ii. Clinical chemistry: creatinine, creatine kinase, urea (or blood urea nitrogen), aspartate aminotransferase, alanine aminotransferase, gamma glutamyltransferase, alkaline phosphatase, lactate dehydrogenase, total bilirubin, albumin, total protein, sodium, potassium, chloride, glucose, uric acid, total cholesterol, magnesium, calcium, phosphorus.
- j. Erythrocyte sedimentation rate should be performed locally.
- k. Urinalysis: color, appearance, specific gravity, pH, protein, glucose, ketones, bilirubin, blood, urobilinogen, nitrite, leukocyte esterase with reflex testing for microscopic parameters.
- l. Quantitative immunoglobulins: IgG, IgM, IgA.
- m. Autoantibodies could potentially include the following: myositis autoantibodies: anti-Jo-1, anti-PL-7, anti-PL12, anti-EJ, anti-OJ, anti-SRP, anti-Mi-2 α , anti-Mi-2 β , anti-MDA-5, anti-TIF-1 γ , anti-NXP-2, anti-HMGCR; other autoantibodies: anti-PM-Scl, anti-U1RNP, anti-SSA, anti-SSB, anti-Ku, anti- SAE, anticentromere, antinuclear.
- n. Pharmacokinetics will be performed as sparse sampling before dosing and at 0.5 (\pm 5 minutes) and 4 hours (\pm 10 minutes) after dosing in all patients at Week 16. In addition, a PK sample will be obtained at 0.25 (\pm 5 minutes), 1 (\pm 10 minutes), or 2 hours (\pm 10 minutes) after dosing at Weeks 16 based on the random assignment of a patient via the Randomization and Trial Supply Management system to PK Cohort A, B, or C.
- o. Blood sampling for PD (proteasome inhibition) will be performed in all patients before dosing and at 4 hours after dosing at Week 16 and at Week 32.
- p. Blood sampling will be performed before dosing at Weeks 16 and 20 and at Week 32 to measure cytokines including IFN α , IFN β , IFN γ , IL-2, IL-6, IL-12, IL-17A, IL-21, IL-23, CXCL10, BLyS, TNF α , TGF β ; and to profile immune cells including B cell subgroups (naïve, activated, memory), plasma cell subgroups (long, short-lived), T cell subgroups (CD4 [Th1, Th17, all, naïve, activated], CD8 [memory], Treg).
